## **HPV test result follow up**

The requesting clinician was responsible for the follow up of HPV results and ensuring participants received their test result. Where appropriate, participants were informed using their preferred method of contact. Participants who received an unsatisfactory or invalid result were asked to repeat their HPV test.

Guidance for the follow up of HPV test results in this study is outlined in Figure 3.

**Figure 3. Study guidelines for the management of HPV results**

*ASCUS: Atypical Squamous Cells of Undetermined Significance, HPV: high risk human papillomavirus, NCSP: National Cervical Screening Programme*

### **Figure 3 details**

*\*Note if a vaginal self-test is taken and the result is positive a cervical cytology specimen is indicated to stratify risk, however in some circumstances it will not change so is not required (i.e., HPV16/18 positive). If a cervical test has been taken this will be performed on the same specimen by the laboratory. It is advised that this test is performed within 2 weeks.*

*\*\*With the new five yearly screening interval, those coming in for their next screening test (after previous cytology screening) any time in the last five years before age 69, i.e., 65 – 69 years of age (inclusive), can exit the programme if their HPV test result is negative. This includes those with normal screening histories, with no screening history, and those with previous abnormalities who have already been returned to regular interval (three yearly) screening. See protocol for details of exceptions.*

[figure not shown]
*Those who would normally exit the NCSP under the current NCSP exit requirements i.e., have had two normal screening cytology samples between ages 62 and 69 years of age, can exit at 69 years of age without HPV testing (providing not immune deficient or requiring further follow-up because of abnormal results).*

*\*\*\*Urgency of referrals to Colposcopy are as follows;*

- *Very Urgent – Suspicion of Malignancy (10 working days)*
- *Urgent – High-grade cytology and/or HPV 16 or 18 positive (20 working days)*
- *Semi-Urgent – Other high-risk HPV and low-grade/ASCUS cytology (3 months)*
- *Colposcopy can be referred as a clinical override e.g., HPV other and patient declining cytology triage.*

Positive clinician-taken LBC cervical HPV samples had cytology performed by the laboratory. The result was sent to the requesting clinician and study staff, as well as directly to the NCSP by the laboratory. Positive HPV vaginal self-test samples cannot have cytology performed on them, so a separate clinician-taken cytology test at the participant's general practice was recommended.

Indications for colposcopy are outlined in Figure 4. Colposcopy was performed as per standard practice guidelines.

**Figure 4. Recommendations for colposcopy management**

*GP: General Practitioner, HPV: high risk human papillomavirus, MDM: Multidisciplinary Meeting.*

On completion of the study, participants were referred back to the NCSP for ongoing follow up. Enrolled patients who were due or overdue for screening and were not screened by the end of the study were referred to the NCSP and screening support services as per standard regional practices.

## **Participant support and education**

Throughout the study, participants could access information on the study website, including the text and audio of the Participant Information Sheet and self-test instructions (Figure 1 and Appendix Figure A4). Additionally, contact details were provided for an independent disability advocate, cultural support, the study nurse, and the study clinical lead.

## **Costs to participants**

Participants could be charged by their general practice for their HPV test and, if required, a subsequent cytology test. As is standard practice in New Zealand, cervical screening is not fully funded. Participants could be charged for their testing at a fee no more than the usual practice fee for cervical cytology. Regional 'support to screen' funding could be utilised to subsidise or cover the cost to patients. Taking part in this study did not interfere with access to this support.

Study funding was provided to participating GP clinics and PHOs to cover the time and resources required to provide study information for full informed consent and to perform

data entry. This cost was not passed on to patients. Patients are not charged for colposcopy in the New Zealand public health system.

## **Safety processes**

The study team provided reminders to general practices and/or PHOs when participants had returned an HPV sample and were overdue for further investigations or repeat testing during the study period (Figure 3). They also checked results to ensure management recommendations are correct. Authors PS, CI, AM, and RB had access to identifiable participant data.

## **Sample size**

It was estimated that the average New Zealand general practice would have 266 patients due for cervical screening over a six-month period and 25% of patients would decline participation in this study. As a result, approximately 15 general practices would be required to recruit 3,000 patients over a six-month screening period. Based on studies investigating the acceptability of vaginal HPV self-testing,[5, 12-14] it was estimated that 60-70% of participants would opt for a vaginal HPV self-test (1,800-2,100 participants). Results from a previous study[3] suggested that approximately 12% of HPV self-tests would be positive, which could result in an estimated 216-252 participants being invited to return to their general practice for cervical cytology. With a sample size of 216 participants with a positive HPV result, there was 95% power to observe a failure to return rate of 2% or more. This is one of multiple clinically meaningful outcomes measured in this study (Figure 2). As this outcome

requires the largest sample size, it was used to determine that recruitment of 3,000 participants would be required.

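### The stated 95% power does not follow from 216 HPV-positive self-testers and a 2% failure-to-return rate, and it does not show that 3,000 participants are required

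*Protocol*

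**What the plan says.** The Sample size section of the protocol argues in this order:

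- Recruitment: an average practice has 266 patients due in six months and 25% decline, so about 15 practices give 3,000 participants.
- Test choice: it expects that "60-70% of participants would opt for a vaginal HPV self-test (1,800-2,100 participants") and that "approximately 12% of HPV self-tests would be positive", which gives "an estimated 216-252 participants being invited to return to their general practice for cervical cytology".
- Power: for 216 HPV-positive self-testers, the lower end of that range, it states that "there was 95% power to observe a failure to return rate of 2% or more".
- Conclusion: among several outcomes of interest, this one "requires the largest sample size, it was used to determine that recruitment of 3,000 participants would be required".

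The section does not say how many failures must be seen, what rate the 2% is compared with, or at what significance level. The Statistical analysis section plans counts and percentages with 95% binomial confidence intervals and names no test for this outcome.

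**The concern.** A power figure needs a decision rule, and none is given here. The only operative word is to observe. The reader therefore has to guess what the 95% refers to, and the obvious guess does not return 95%.

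This is the only power statement in the protocol and the only statistical reason offered for the sample size. Two things are at stake. A reader may credit the study with a property that was not correctly calculated. The claim that this calculation led to 3,000 may also be carried into the report, since analysis was in progress when the document was written. The protocol states the figure itself, so this is not a detail left to a later analysis plan.

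**Working it through.** **Inputs (all from Sample size):** 266 patients due per practice, 25% declining, 15 practices, N = 3,000, 60-70% self-testing, 12% positivity, n = 216, failure-to-return rate 2%, stated power 95%.

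**1. The protocol's forward arithmetic reproduces.**
- 266 × 0.75 × 15 = 2,992.5, about 3,000.
- 3,000 × 0.60 × 0.12 = 216; 3,000 × 0.70 × 0.12 = 252.

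This chain starts from 3,000. It does not arrive at it.

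**2. The 95% on the plainest reading: at least one failure is seen.**
- P(X ≥ 1) = 1 − (1 − p)^n = 1 − 0.98^216 = 1 − 0.0127 = 98.7%.
- For true rates above 2% the probability is higher still, so 98.7% is the minimum for "a failure to return rate of 2% or more".

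**3. What 95% would correspond to on that reading.**
- Rate, with n = 216: p = 1 − 0.05^(1/216) = 1.38%.
- Positives, with p = 2%: n = ln 0.05 / ln 0.98 = 148.3, so 149.
- Participants for 149 positives: 149 / (0.12 × 0.60) = 2,069.4, so 2,070; 149 / (0.12 × 0.70) = 1,773.8, so 1,774.

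**4. Other event rules at a true rate of 2% (exact binomial).**

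| Rule | n = 216 | n = 234 (65% self-test) | n = 252 |
|---|---|---|---|
| At least 1 | 98.7% | 99.1% | 99.4% |
| At least 2 | 93.1% | 94.9% | 96.2% |
| At least 3 | 80.8% | 84.8% | 88.1% |

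At 216 the probability drops from 98.7% to 93.1% as the rule moves from one failure to two, so no minimum-count rule gives 95% there. At-least-two first reaches 95% at 236 positives. That is 236 / (0.12 × 0.60) = 3,278 participants at 60% self-testing and 236 / (0.12 × 0.70) = 2,810 at 70%.

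**5. Reading it as a test against a null rate.** The protocol gives no null, so these are assumptions. Exact one-sided tests with n = 216 and a true rate of 2%, at a significance level of 0.05, have power 98.7% against a null of 0.01%, 93.1% against 0.05% or 0.1%, 62.9% against 0.5% and 26.6% against 1%. None is 95%.

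**6. What 216 gives under the planned analysis.** An observed 4/216 is 1.85%. The exact (Clopper-Pearson) limits are the 2.5% point of Beta(4, 213) and the 97.5% point of Beta(5, 212), that is 0.5% to 4.7%.

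**The case against.** The best defence is that the figure is near enough and errs on the safe side. Much of this stands.

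- **Some rule does come close.** At-least-two gives 93.1% to 96.2% over the protocol's own 216-252 positives, and the participants it implies for 95% (2,810 to 3,278) include 3,000. A reader might infer that no sensible reading approaches 95%, and that would go too far. But the rule is not in the protocol, and at the stated 216 it falls 1.9 points short.
- **The plainest reading favours the study.** It gives 98.7%, so 95% is an understatement. A reader might infer that the sample is too small. The 149 positives show a surplus for that aim.
- **The literal reading is poor evidence.** The chance that the observed rate is itself at least 2% (5 or more of 216) is 43.4% at a true rate of 2%. A reader might take that as the real power. A value near one half is expected for almost any n when the true rate equals the threshold, so this is unlikely to be what was meant.
- **Clustering by practice.** A reader might add that patients within practices are not independent. The protocol gives no intracluster correlation, so no size can be put on this and the point does not rest on it.
- **Little depends on the 2%.** The study is single-arm and descriptive, failure to return is not one of the three primary outcomes, and no decision threshold uses 2%. This limits the importance of the error.

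What the defence does not answer is that nothing stated in the protocol yields 95% at 216, or makes 3,000 the required number.

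**Conclusion.** The statement is wrong as written, with limited consequences. On the plainest reading the probability is 98.7%, not 95%, and the stated 95% would need only 149 positives, or about 1,774 to 2,070 participants. What fails is the claim that 95%, 2% and 216 determined 3,000. The recruitment arithmetic behind 3,000 is sound and is a feasibility basis in its own right.

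The figures assume independent participants, a true rate of exactly 2%, and the protocol's own 12% positivity and 60-70% self-testing.

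A reader might infer from the word power that the study can establish whether failure to return is above or below 2%. The documents do not support that: they plan an interval, not a test, and 4/216 would be compatible with 0.5% to 4.7%.

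Recruitment was complete by January 2024 and no test depends on the 2%, so this is a correction to make before the sample-size rationale is reported. It does not threaten the results.

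**What to change.** Mark both changes as corrections, so that the original rationale stays visible.

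1. Replace the power sentence with:

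> With 216 HPV-positive self-testers, the probability of observing at least one failure to return is 98.7% if the true rate is 2% (95% if it is 1.4%). An observed rate of about 2% (4/216) would have an exact 95% CI of about 0.5% to 4.7%.

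2. Replace the claim that this outcome determined the sample size with a statement that 3,000 is a feasibility target (about 15 practices × 266 × 75%) that yields this precision.

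If the sponsor did use another rule, such as at least two failures or a test against a stated null, it should state that rule and give the probability that goes with it at 216.

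The cost is two sentences of text, with no change to enrolment, data collection or analysis. The sample size loses its claim to a power calculation and is described instead by the precision it gives.

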## **Outcome measures and data management**

The study outcome measures are presented in Figure 2. For further details, see Appendix Table A1.

Staff from participating general practices and PHOs entered data from participants into a secure REDcap database. Study staff also collected:

- Screening data from the NCSP.
- HPV and cytology results from the study laboratory.
- Colposcopy results from hospital records.
- Human papillomavirus vaccination status from the Ministry of Health National Immunisation Register, for participants who specifically consented to have this data collected.
- Socioeconomic status (through coding of street addresses to the New Zealand Index of Deprivation).[15]
- Proximity to health services (through coding of street addresses to Statistics New Zealand's urban accessibility classification[16] and the Geographic Classification of Health).[17]

Participants could opt to withdraw from the study at any time. Data collected up to the point of withdrawal was kept and processed. Data was anonymised prior to analysis.

At the completion of the study, participating general practices and/or PHOs were to provide the total number of their patients identified as being due or overdue for screening during the study period. Deidentified data from patients that did not take part in the study was also collected, including detail on attempts to invite them for screening, demographics, screening history, and whether they had cervical cytology during the study period. For further detail see Appendix Table A1.

## **Statistical analysis**

Statistical analyses will be performed using R[18] and STATA.[19] Discrete endpoints will be summarised as counts and percentages with 95% binomial confidence intervals (CI). Continuous variables will be displayed graphically, and summarised as means with 95% CI and standard deviations or medians and interquartile ranges as appropriate. Time to event data with censoring will be displayed using Kaplan-Meier or cumulative density plots. Outcomes will be stratified by participants' choice of self-taken vaginal HPV or clinician-taken cervical HPV test and/or other variables of interest such as screening history, age, self-reported ethnicity, socioeconomic status, and region (further details are available in Table A1 of the Appendix).

## Results dissemination

Results will be deidentified prior to dissemination. A report will be forwarded directly to the NCSP. Results will be disseminated to cultural consultation groups and to groups involved in locality approval, trial registration, and ethical approval of the study. Importance will be placed on communicating results to local iwi and community groups supporting the study. Participants and study sites will be sent a summary of the overall results if they opt for this. Results will be submitted for publication in a peer reviewed journal and may be presented at academic conferences.

## Discussion

---

This study will evaluate the impacts of implementing primary HPV-based cervical cancer screening, including the option of a self-test, in the New Zealand primary care setting. It is designed to give pragmatic and detailed information regarding screening participation and the impact on services that will occur with the introduction of HPV testing. It provides a unique opportunity to directly inform nationwide recommendations and practice.

It is well established that screening with primary HPV testing is more sensitive than primary screening with cervical cytology, and that self-testing offers opportunities to reduce barriers and improve participation in cervical screening.[2-7] However, the introduction of primary HPV testing is a significant change to the prior cervical screening process in New Zealand. Therefore, in this implementation study, we enable a range of primary care organisations to

offer eligible people the choice of a vaginal HPV self-test or a clinician-taken HPV sample. We collected data to observe which tests were selected, the resources required to complete the screening and diagnostic pathway, HPV test results, and engagement with the triage and diagnostic pathway.

Measures to ensure the engagement of local populations need to be individualised and tailored to the resourcing and health systems where the HPV screening program takes place. In New Zealand, most cervical cancer screening is delivered by primary care practices and people pay for their screening, although funding to support some priority groups is available. Laboratory tests and specialist gynaecology care are provided for free. General practices participating in this study may opt to charge their patients for cervical screening as part of their standard practice, reflecting what occurs in the clinical setting.

While New Zealand had a well-established and successful cervical cytology-based screening program, outcomes were inequitable.[1] In recognition of this, the study team includes Māori and Pacific steering groups, who have worked to ensure that the study is as equitable as possible, cultural safety is upheld, and recruitment is representative of Māori and Pacific people in New Zealand. Additionally, the selection of participating general practices has been designed to maximise adequate representation of Māori and Pacific people.

In this study, tests can only be ordered by accredited smarttakers. This is to ensure the clinical safety of participants. In order to take full advantage of the portability of the self-test,

community health workers (and kaiāwhina) and other health professionals may need to have the option to arrange screening tests themselves, however this is beyond the scope of the current study.

This research does not sit in isolation; there were two other implementation studies running concurrently in New Zealand, focussing on different demographics and methodologies.[20] All three studies will provide a collective evidence base to inform the practical aspects of the national roll out of HPV testing. In addition, multiple international screening programs utilise HPV testing including the option of a self-test. This study is unique with regards to participant population, the context of the New Zealand health system, the requirement for most participants to pay to access their screening test, and the ability for participants to choose a clinician-taken cervical HPV test or a vaginal HPV self-test. Information from this study, along with data from other local studies and international cervical screening programs will inform the NCSP of the important issues that can be anticipated with the introduction of their HPV screening program.

## Conclusions

---

This study is designed to provide a clinically relevant evidence-base from which practical recommendations can be made to optimise the introduction of primary HPV testing for cervical screening in New Zealand. These recommendations have the potential to improve

health outcomes, guide resource allocation, and identify factors that could reduce inequities in the cervical screening programme.

# Appendix

---

## Table A1. Full list of study outcomes

Please note, as appropriate, data will be presented separately by whether the participant opted for:

- Vaginal high risk human papillomavirus (hrHPV) self-test performed at home or other suitable location
- Vaginal HPV self-test performed at the general practice with or without support/assistance from a nurse or doctor.
- Clinician-taken cervical HPV test.

Outcomes relate to all participants unless otherwise stated.

---

### Primary outcome 1

The number (and percentage) of participants that undertook a:

- Vaginal test at home
- Vaginal test at their General Practice (GP) clinic without staff assistance
- Vaginal test at their GP clinic with staff assistance
- Cervical test without concurrent cytology
- Cervical test with concurrent cytology.

Data obtained from participating GP clinics.

*Timepoint:*

By the end of screening period.

---

### Primary outcome 2

The number (and percentage) of participants who had the following high risk human papillomavirus (hrHPV) result:

- HPV 16
- HPV 18
- Other hrHPV (listed by genotype where available)
- hrHPV not detected.

Data obtained from participating GP clinics and laboratories.

*Timepoint:*

By six months after the end of the screening period.

---

### Primary outcome 3

The mean, median and range for the time between an hrHPV test report being issued and GP referral for colposcopy in all participants that had an hrHPV result that indicated requirement for referral to colposcopy.

Data to be presented separately by whether participants had a cervical or vaginal hrHPV test, and whether the referral was made with or without cytology results.

Data to also be presented separately for participants negative for hrHPV, participants positive for human papillomavirus (HPV) 16 and/or 18, and participants positive for hrHPV other than 16 or 18.

Data obtained from participating GP clinics and laboratories.

*Timepoint:*

By six months after the end of the screening period.

---

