#### **Secondary outcome 25**

In participants that had a colposcopy, the mean, median and range for time from GP referral to their colposcopy appointment.

Data to be presented separately for each classification of urgency.

Data to also be presented separately for participants negative for hrHPV, participants positive for HPV16 and/or 18, and participants positive for hrHPV other than 16 or 18.

Data obtained from participating GP clinics and colposcopy clinics.

*Timepoint:*

By six months after the end of the screening period.

---

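### Primary outcome 3 names a population that two of its three HPV strata do not fit, and its timing statistics leave out anyone never referred

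*Protocol*

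**What the plan says.** **Outcome.** Protocol, Table A1, Primary outcome 3 asks for "The mean, median and range for the time between an hrHPV test report being issued and GP referral for colposcopy", taken "in all participants that had an hrHPV result that indicated requirement for referral to colposcopy". Results are to be split by cervical or vaginal test and by "whether the referral was made with or without cytology results". A further split follows: "Data to also be presented separately for participants negative for hrHPV, participants positive for human papillomavirus (HPV) 16 and/or 18", and those positive for other types.

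**Basis for referral.** The legend to Figure 3 lists the referral categories. One is "Urgent – High-grade cytology and/or HPV 16 or 18 positive (20 working days"). Other high-risk HPV appears together with low-grade or ASCUS cytology, and a clinical override is allowed, for instance when a person with other HPV declines triage. Positive cervical samples have cytology done by the laboratory on the same specimen. Positive self-test samples cannot, so a separate clinician-taken sample is recommended.

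**Analysis.** The Statistical analysis section says: "Time to event data with censoring will be displayed using Kaplan-Meier or cumulative density plots". It does not name the outcomes this covers. Figure 2 words the same primary outcome as a distribution of times and states no population.

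**Follow-up.** Figure 1 details give three months after the six-month recruitment period closes. Table A1 gives six months after the screening period ends.

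**The concern.** This is one of three primary outcomes, and Table A1 itself fixes its population, strata and statistics. They do not fit together, so two analysts following the text could build different denominators.

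The statistics add a second problem. A person who needed referral and never received it has no time to average, so that person contributes nothing to the timing summary. The gap between a positive self-test and triage is the part of the pathway on which the study was sized, and a summary of completed referrals cannot show a failure there.

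The planned split by test type could also be uneven. Suppose the indication is read as HPV plus cytology. A self-tester with other HPV who is lost before triage then has no indication and leaves the denominator. A cervical tester already has cytology and cannot be lost at that step.

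**Working it through.** **1. Population against strata (no assumptions).** The population requires that the HPV result itself indicated referral.

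| Stratum in Table A1 | Basis for referral in Figure 3 details | Fits the population? |
|---|---|---|
| HPV 16 and/or 18 | HPV result is sufficient | Yes |
| Other HPV | HPV plus abnormal cytology, or override | Not on the HPV result alone |
| HPV negative | Possible only on cytology or suspicion of malignancy | No |

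The flowcharts of Figures 3 and 4 are not in the text available, so this rests on the Figure 3 legend.

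**2. Statistics against population.** As written, the population includes people who were not referred. A mean or range of time to referral does not exist for them, and the split by whether cytology accompanied the referral is defined only once a referral has been made. Table A1 gives no rule for the remainder.

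**3. The protocol's own planning figure.** The Sample size section expects 216 to 252 positive self-testers to be invited back for cytology. This reproduces: 3,000 × 0.60 × 0.12 = 216 and 3,000 × 0.70 × 0.12 = 252. At the 2% failure-to-return rate named there, 216 × 0.02 = 4.3 and 252 × 0.02 = 5.0 people would not return. The section does not split these positives by HPV type, so the number with other HPV is not known.

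**4. Size of the shift in the median.** Let *f* be the fraction of those needing referral who are never referred, and *F* the distribution of times in those who are. By time *t*, the fraction referred among all who need it is (1 − *f*)·*F*(*t*). Setting this to 0.5 gives *F*(*t*) = *q*, with *q* = 0.5/(1 − *f*). The median over everyone, divided by the median in the referred, is then:

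- exponential times: −ln(1 − *q*)/ln 2
- lognormal times with log-SD 1: exp(*z*), where *z* is the standard normal quantile of *q*

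At *f* = 0.10, *q* = 0.5/0.9 = 0.556. The exponential ratio is 0.811/0.693 = 1.17 and the lognormal ratio is exp(0.140) = 1.15.

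| *f* | *q* | Exponential | Lognormal |
|---|---|---|---|
| 2% | 0.510 | 1.03 | 1.03 |
| 5% | 0.526 | 1.08 | 1.07 |
| 10% | 0.556 | 1.17 | 1.15 |
| 20% | 0.625 | 1.42 | 1.38 |
| 30% | 0.714 | 1.81 | 1.76 |

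At *f* of 50% or more the median over everyone is not reached. Both *f* and the distributions are assumptions, because the protocol gives neither.

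**5. Effect of the cut-off date.** The inclusion criteria allow participation up to three months after recruitment, so tests may fall over nine months. Figure 1 details then put the end of follow-up at month 9. Table A1 puts it at month 12, if the screening period is the six months stated in Secondary outcome 37. Assume uniform test dates and exponential times with a mean of one month. The share of referrals seen by month 9 is 1 − (1 − e⁻⁹)/9 = 0.889. By month 12 it is 1 − (e⁻³ − e⁻¹²)/9 = 0.994. In simulation the median in those seen is 0.61 months at the first cut-off and 0.69 at the second, against a true 0.69.

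**The case against.** A reader might infer that the outcome is restricted to people who were referred. The text does not say so: the stated set is everyone whose result indicated referral. The restriction comes from the statistics chosen. Unreferred HPV 16/18-positive participants could be censored and a median read from a curve, and the statistical analysis plan, which is not at hand, may say this. That is fair, but it would not repair the mismatch between population and strata that Table A1 sets out.

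A reader might also infer that lost self-testers disappear from the results. They do not. Completion of each step is a stated objective in Figure 2. Secondary outcome 15 counts cytology invitations, outcome 16 gives reasons for missing cytology after a positive vaginal test, and outcome 23 counts referrals by HPV group. None of these gives referral by a fixed time. Among people with other HPV, outcome 23 does not separate negative triage from unresolved loss.

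The uneven loss by test type is narrower than it first appears. It mainly concerns other HPV, because HPV 16/18 self-testers can be referred without cytology. It depends on reading the indication as HPV plus cytology. On the literal wording, other HPV fails to qualify in both test groups. Clinical override can also bring back some who decline triage.

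Nor do the documents establish a material bias. The only failure-to-return figure is 2%, where the shift is about 3%. That figure is a rate the study should be able to observe, not a forecast, so it does not rule out a larger loss.

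Finally, Secondary outcomes 17, 22 and 25 condition openly on the event, as in "In participants that had a colposcopy, the mean, median and range for time from GP referral to their colposcopy appointment". They are legitimate turnaround times and are not errors.

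**Conclusion.** The point stands as a defect in the definition of a primary outcome. Two of its three HPV strata do not match the stated population. That finding needs no assumption beyond the Figure 3 legend.

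The named statistics describe completed referrals only, so the time to referral is understated whenever people who need referral are not referred or are referred after the cut-off. The direction is clear, but the protocol does not determine the size. The effect on the median is negligible at 2% non-referral and becomes material from about 10%, under the assumed distributions. These factors concern people known to need referral. For a self-tester with other HPV who is lost before cytology, need is unknown, and the factors do not measure that loss.

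**What to change.** Define two sets, each with the clock starting at the HPV report.

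- **All HPV 16/18-positive participants:** one minus the Kaplan-Meier estimate for referral.
- **All participants positive for other HPV only:** cumulative incidence of referral, with a negative cytology triage result as the competing event and unresolved people kept in. This is a proportion of all with other HPV, and its median may not be reached.

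Report the percentage referred at fixed days, and the median where reached, by test type. Drop the HPV-negative stratum, or report those referrals separately with the clock from the cytology report. Label any mean or range, and the split by cytology at referral, as being in those referred. Secondary outcomes 17, 22 and 25 may stay if labelled as conditional on the event.

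State one censoring date by reconciling the three months in Figure 1 details with the six months in Table A1.

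The cost is revised wording and standard survival code. The dates needed are already required for the listed outcomes. The study is prospectively registered and analysis is in progress, so this is a small change to a registered primary outcome's definition and should be disclosed with its date and reason.
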